10.15.4 Serious adverse events

Any adverse event that meets any of the following criteria will be handled as a serious adverse event for all adverse events, including those that occur from the collection of informed consent to before the start of the study treatment. If any serious adverse event occurs, its symptom or laboratory test parameter and the reason for judging it as serious will be recorded in the CRF.

- 1) Death
- 2) Life Threatening
- 3) Initial or Prolonged Hospitalization
- 4) Persistent or Significant Disability/Incapacity
- 5) Congenital Anomaly or Birth Defect
- 6) Other Medically Important Event

Other Medically Important Event is defined as cases that do not immediately threaten life or lead to hospitalization, but may expose patients to danger, or cases associated with medical events that require treatment or procedure to prevent the outcomes listed in the above 1) to 5).

10.15.5 Adverse events of special interest

The following adverse events are considered as an adverse event of special interest (regardless of seriousness). The details of adverse events of special interest are specified in the Statistical Analysis Plan.

- 1) Bleeding-related adverse events
- 2) Gastrointestinal disorders
- 3) Infection
- 4) Hypertension

- 5) Neutropenia
- 6) Hepatic dysfunction
- 7) Thrombosis, embolism, and thromboembolism

10.15.6 Actions taken with the study drug

Actions taken with the study drug are defined in Table 10.15.6-1.

Table 10.15.6-1 Actions Taken with the Study Drug

10.10.0-1	Actions raken with the olday brag
Action	Definition
Drug withdrawn	Discontinuation of the study treatment due to the adverse event in question, including the
	discontinuation requested by the subject
Drug interrupted	Interruption of the study drug due to the adverse event in question, including the
	interruption requested by the subject
Dose Reduced	Dose reduction of the study drug due to the adverse event in question, including the dose
	reduction requested by the subject
	Inability to increase the dose of the study drug due to the adverse event in question in
	subjects who meet the dose increase criteria
Dose not	Study treatment continued without taking any action to the study drug
changed	
Unknown	Actions taken to the study drug cannot be determined
Not applicable	The administration of the study drug is completed or discontinued before the onset of the
	adverse event in question

10.15.7 Outcome of the adverse event

The outcome of adverse events will be assessed according to Table 10.15.7-1.

Table 10.15.7-1 Outcome of the Adverse Event

Outcome	Decision criteria
Recovered/Resolved	Resolution of or recovery from symptoms, normalization of test values, or recovery
	to the baseline level
Recovering/Resolving	Reduction or improving tendency of the severity of symptoms or abnormal values
Not Recovered/Not	Almost no change or exacerbation in symptoms or abnormal values
Resolved	
Recovered/Resolved	Dysfunction derived from symptoms or abnormal values and interfering with
with Sequelae	activities of daily living
Fatal	Death related to symptoms/abnormal values
	*This outcome should not be chosen for death not related to symptoms or abnormal values.
Unknown	Inability to follow the outcome despite every possible effort to follow symptoms and
	abnormal values

10.15.8 Causal relationship between adverse events and the study drug

The causal relationship of adverse events with the study drug will be assessed on a 2-point scale according to Table 10.15.8-1, considering the condition of subjects, complications, medical history, concomitant drugs, and temporal relationship with the onset. Of adverse events that develop after the start of the study treatment, those evaluated as "Yes" for the causal relationship with the study drug are considered to be an adverse drug reaction.

For adverse events secondary to another adverse event, the causal relationship with the study drug should be evaluated for each adverse event independently.

Version: 1.0

Table 10.15.8-1 Causal Relationship between Adverse Events and the Study Drug

Relationship	,
to study	Decision criteria
treatment	
Related	An adverse event is considered to have a causal relationship with the study drug because, for example, the onset of the adverse event can be easily explained from the condition of the subject, complications, medical history, concomitant drugs, or temporal relationship with the onset of the adverse event.
Not related	 An adverse event does not meet the above decision criteria for the causal relationship with the study drug because it meets any of the following criteria. The adverse event is clearly attributable to a factor other than the study drug. There is no temporal correlation between the onset/resolution of the adverse event and administration of the study drug and there is a long interval between them. The occurrence of the adverse event is considered incidental (eg, the same event has been frequently observed since before the study and the adverse event that occurred during the study is considered to be one of them). There are possible factors other than the study drug, such as the medical history/condition of the subject or other concomitant drugs/measures, treatment, and meals.

10.15.9 Follow-up

Among serious adverse events that occur from the collection of the informed consent to before the start of the study treatment and adverse events that occur after the start of the study treatment, those for which symptoms are not resolved or improved to the level before onset by the end of the follow-up period as judged by the investigator will be followed. Follow-up will be terminated in either of the following cases.

- 1) The event is improved or resolved, as judged by the investigator.
- 2) The event no longer requires additional follow-up, as judged by the investigator.

10.16 Evaluation of Diarrhea

When diarrhea occurs as an adverse event, the grade of diarrhea according to Common Terminology Criteria for Adverse Events (CTCAE) Ver. 5.0 (see Appendix 5), duration of onset by grade, and actions taken with the study drug will be recorded in the CRF to confirm the appropriateness of dose adjustment of the study drug.

11. Schedule of Study Assessments and Procedures

The investigator and clinical research coordinator will perform the specified study assessments and procedures according to the study schedule and "10 Study Assessments and Procedures."

11.1 Collection of Informed Consent

- Written informed consent
- Inclusion/exclusion criteria
- First registration

Version: 1.0

11.2 Screening Period

11.2.1 Visit 1 (Screening A)

- Demographics
- ITP Bleeding Score
- Adverse events/concomitant medications
- ECOG Performance Status
- 12-lead ECG^{a)}
- Vital signs
- Laboratory tests (hematology, serum chemistry, urinalysis, D-dimer assay,^{b)} PT-INR/APTT)
- Immunoglobulin test
- Immunological test
- Pregnancy test (women of childbearing potential only)
- Inclusion/exclusion criteria
- Second registration
- a) In principle, the 12-lead ECG is taken before vital signs, laboratory tests, immunoglobulin test, immunological test, and pregnancy test (women of childbearing potential only).
- b) D-dimer assay is performed if the patient has a history of venous thromboembolism more than 6 months prior to Screening A.

11.2.2 Visit 2 (Screening B)

- Demographics
- Adverse events/concomitant medications
- Vital signs
- Laboratory test (Hematology)

11.3 Period I

11.3.1 Visit 3 (Day 1)

- QOL evaluation (SF-36)^{a)}
- Demographics
- ITP Bleeding Score
- Adverse events/concomitant medications
- ECOG Performance Status
- Height and weight

- Vital signs
- Laboratory tests (hematology, serum chemistry, urinalysis, and PT-INR/APTT)
- Immunoglobulin test
- Inclusion/exclusion criteria
- Third registration
- Study drug dispensed (Period I)
- Administration of study drug
- a) The QOL evaluation (SF-36) is performed before other procedures and evaluations.

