- 27) Pregnant patients, breast-feeding patients, patients who wish to become pregnant during the period from informed consent to 30 days after the last dose of the study drug, or women who are not willing to use appropriate methods of contraception.
- 28) Patients who have received other study drugs within 12 weeks before acquisition of consent.
- 29) Other patients whom the investigator judges to be inappropriate for the study.

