5.2.2 Rationale for exclusion criteria

1) to 3) These criteria were set to exclude patients ineligible for the study.

4), 14), 16), 17), 19) These criteria were set to exclude the matters that might affect the efficacy evaluation of R788.

5) to 13), 15), 18), These criteria were set to ensure the safety of subjects.

20) to 25), 28)

This criterion was set to eliminate the effect on the efficacy evaluation of R788 and compliance with the protocol.

Animal studies have reported that R788 has embryofetal toxicity and migrates into breast milk. This criterion was set to avoid the administration of R788 in pregnant or lactating patients.

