8.6 Dose and Administration

8.6.1 Dose and administration

Dose and administration method are shown in Figure 8.6.1-1 and Figure 8.6.1-2.

1) Screening period

No study drug is administered.

2) Period I

R788 or matching placebo is administered orally for 24 weeks. On Day 1, 100 mg of the study drug will be administered at the study institution. This must be the only administration of the study drug on Day 1, irrespective of the time of administration. The study drug will be administered twice daily beginning on the next day and the dose will be adjusted according to "8.6.2 Dose adjustment" during Period I. Morning and evening doses should be at least 8 hours apart and should be taken at approximately the same time each day, with or without food during Period I. In principle, subjects will visit the study institution in the morning without taking the study drug and take the study drug at the study institution in the morning to measure drug concentration at Weeks 2 and 6. In principle, subjects will take the study drug at 1 to 4 hours before visiting the study institution in the morning at Week 4 and Weeks 8 to 24.

3) Period II

R788 is orally administered for 28 weeks.

(1) Subjects who completed Period I

The study drug for Period I is continued until the visit at Week 24 and the study drug for Period II is initiated after the visit at Week 24 (if study drug in Period II is initiated as twice daily, subjects who took the study drug for Period I in the morning on the day of the visit start the study drug for Period II from the evening of the same day). The dose and administration at the start of the study drug for Period II is as follows.

- If platelet count at Week 24 is $\geq 50000/\mu$ L, study drug in Period II is initiated with the last dose and administration in Period I.
- If platelet count at Week 24 is $< 50000/\mu$ L and last dose and administration in Period I is 150 mg *bid*, study drug in Period II is initiated with 100 mg *bid*.
- If platelet count at Week 24 is $< 50000/\mu$ L and last dose and administration in Period I is 100 mg qd, 150 mg qd, or 100 mg bid, study drug in Period II is initiated with the last dose and administration in Period I.

(2) Early transition subjects

The study drug for Period II is initiated after the visit on ET Day 1 (if study drug in Period II is initiated as twice daily, subjects who took the study drug for Period I in the

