8.8.4.3 Third registration

The investigator will make the last confirmation of eligibility of each subject on Day 1, fill in the third registration form, and promptly perform the procedure to register the subject.

The Subject Registry Center will notify the investigator of whether to accept the third registration or not. The completed third registration form and third registration confirmation form obtained from the Subject Registry Center will be stored at the study institution. In addition, the investigator will inform the Subject Registry Center of the reason subjects who

were considered eligible at the second registration were not considered eligible at the third registration.

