10.12 Pregnancy Test

Pregnancy test (serum human chorionic gonadotropin [HCG]) will be performed in women of childbearing potential (women who have not had their uteri or bilateral ovaries removed and had their last menstrual within 1 year) in the designated central laboratory. The presence or absence of sampling and pregnancy will be recorded in the CRF.

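### For women of childbearing potential, the only pregnancy test before the first Period I dose is at Screening A, so the result is 25 to 31 days old on Day 1

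*Protocol*

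**What the plan says.** Protocol 5.2.1, exclusion 27, begins "Pregnant patients, breast-feeding patients, patients who wish to become pregnant during the period from informed consent to 30 days after the last dose". The rationale in 5.2.2 is "Animal studies have reported that R788 has embryofetal toxicity and migrates into breast milk". Under 8.8.4.3, "The investigator will make the last confirmation of eligibility of each subject on Day 1". Under 8.6.1, "On Day 1, 100 mg of the study drug will be administered at the study institution".

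The test is defined in 10.12: "Pregnancy test (serum human chorionic gonadotropin [HCG]) will be performed in women of childbearing potential", and the same sentence assigns it to the designated central laboratory.

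The visit lists in section 11 place it as follows:

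- **Screening A (11.2.1):** "Pregnancy test (women of childbearing potential only" is listed.
- **Screening B (11.2.2):** the only laboratory entry is "Laboratory test (Hematology".
- **Day 1 (11.3.1):** the laboratory entry is "Laboratory tests (hematology, serum chemistry, urinalysis, and PT-INR/APTT". An immunoglobulin test is also listed, but no pregnancy test. The chemistry panel in 10.5.2 does not contain HCG.
- **After Day 1:** the test is listed at Week 12 (11.3.7), Week 24 (11.3.13), ET Day 1 (11.5.1), the Withdrawal Visit (11.8.1) and the end of follow-up (11.9.1).

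The Period I schedule table agrees with section 11, so this is not one incomplete list.

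**The concern.** Eligibility is settled on Day 1, and pregnancy is an exclusion because of a hazard to the fetus. Yet the newest scheduled evidence on pregnancy at that moment comes from the start of a four-week screening period. Two kinds of pregnancy would be missed: one that begins after Screening A because contraception fails, and one already present at Screening A but too early for the test to show. Contraception is required only from informed consent (section 9, item 16), so it cannot prevent a conception shortly before consent.

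The women directly at stake are those randomised to R788. Their exposure could continue until pregnancy is suspected or until the next scheduled test. The protocol treats such exposure as serious: 12.3 calls for follow-up to delivery and of the child to about 1.5 years of age. This is a matter of subject safety and does not bear on any estimate or test.

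**Working it through.** **Inputs.** The visit windows are in the Period I schedule table: Screening A Day -31 to -25, Screening B Day -17 to -11, Week 12 Day 82 to 88. SAP Table 5.9-2 sets the Screening A target at Day -28 and calls the day before first dosing Day -1, so there is no Day 0. Protocol 8.9.1 plans 16 subjects on R788 and 8 on placebo.

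**Formula.** With no Day 0, the time from Day -d to Day 1 is d days. From Day 1 to a later Day k it is k - 1 days.

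**Check on the plan's own figure.** The target Day -28 gives 28 days, which is the four-week screening period of Protocol 8.2.

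**Results.**

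| Interval | Arithmetic | Days |
|---|---|---|
| Screening A to Day 1 (age of the result at first dose) | 25 to 31 | 25 to 31 |
| Day 1 to Week 12 (next scheduled test) | 82 - 1 to 88 - 1 | 81 to 87 |
| Screening B to Day 1 (age under the fallback) | 11 to 17 | 11 to 17 |

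The Week 12 interval is an upper limit on the wait for a scheduled test, because a subject who leaves sooner is tested at the Withdrawal Visit.

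**Numbers affected.** Neither document gives the number of women of childbearing potential. It can be anything from 0 to 16 in the R788 arm and from 0 to 8 in the placebo arm.

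**Comparison with other starts of R788.** The drug is started or restarted at four points: Period I Day 1, Week 24, ET Day 1 and Period III Day 1. A pregnancy test is listed at the last three (11.3.13, 11.5.1, 11.7.1). Only Period I Day 1, the first exposure for the R788 arm, has none.

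**What the existing controls can detect.**

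- Contraception (section 9, items 16 and 17) prevents pregnancy but does not detect it.
- Self-report (section 9, item 16) and stopping on suspicion (12.3) need a suspicion first.
- The Day 1 inclusion and exclusion review (11.3.1) has no scheduled result newer than Screening A.
- Withdrawal for pregnancy (5.3.1, item 5) acts only once the pregnancy is known.
- Demographics, collected again on Day 1, include whether a pregnancy test is needed (10.1, item 9). That may prompt a site, but it does not order a test.

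**Week 24 and ET Day 1.** A sample is drawn at each of these visits and sent to the central laboratory. Under 8.6.1, Period II R788 can start the same evening if dosing is twice daily and the morning Period I dose was taken. No text requires the result first, and the transition criteria in 8.3.1 do not mention pregnancy.

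**The case against.** The best reply is that the protocol is consistent. Eligibility criteria measured centrally are checked at Screening A only (exclusion 11, for liver and renal values), while those measured at the institution are repeated at Screening B and Day 1 (exclusion 10, for blood counts). HCG is central, so it follows the first pattern. The documents set no maximum age for a pregnancy result, contraception is mandatory, women unwilling to use it are excluded, and the number of women concerned could be zero. All of that is true. It explains the schedule and keeps the expected number of events small. It does not supply a way to find an unsuspected pregnancy before dosing.

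The reply also has force on feasibility. The provision in 10.5.2 for additional tests at the institution concerns serum chemistry. Section 10.12 has no such provision, and nothing says that every site can run HCG or how fast. This stands, and it is why a fallback is needed.

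Two stronger readings are tempting and should not be drawn:

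- **That no pregnancy result is needed before the first dose.** The Screening A test is mandatory for women of childbearing potential and is listed ahead of the second registration. What is missing is a fresh result.
- **That Week 24 and ET Day 1 have the same gap, measured by the age of the previous result.** A sample is drawn at both visits. A positive result leads to withdrawal (5.3.1) and prompt discontinuation (12.3). Exposure of a pregnancy that this sample detects is therefore limited by the central laboratory's turnaround, which is not stated, and not by how long ago the last test was. ET Day 1 also lists an inclusion and exclusion check. First exposure to R788 at these visits concerns only placebo subjects, at most 8 as planned.

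**Conclusion.** The point holds for Day 1. Women of childbearing potential are first dosed on a pregnancy result that is 25 to 31 days old, with no fresh test at Screening B or Day 1. The next scheduled test is 81 to 87 days later, or at the Withdrawal Visit if sooner. The day counts rest on visits falling within their windows.

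The likely number of exposed pregnancies cannot be estimated from the documents, which give neither the number of women of childbearing potential nor a pregnancy rate. The case therefore rests on the seriousness of the hazard and the low cost of closing the gap, and not on an expected count.

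The missing result-before-dispensing rule at Week 24 and ET Day 1 is a minor secondary point. No endpoint or analysis changes, so this is a cheap improvement to subject protection and not a flaw in the trial's inference.

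**What to change.** **Main change.** Add an HCG test on Day 1 for women of childbearing potential to the Period I schedule table and 11.3.1. Amend 10.12 so that the study institution may run it. Require in 8.8.4.3 a negative result before third registration and first dose. The result is then from the day of dosing.

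**Fallback.** Where a site cannot run HCG, add a central sample at Screening B. The result is then 11 to 17 days old on Day 1. This is a partial remedy, because it does not re-check on Day 1.

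**Secondary change.** Where an institution-run test is available, require a negative result before Period II drug is dispensed at Week 24 (8.8.4.5) and on ET Day 1 (8.3.1). Apply it to both arms so that the blind is kept.

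**Cost.** The Day 1 test means one added assay per woman of childbearing potential: at most 16 + 8 = 24 among the planned subjects, plus one for any woman who then fails on Day 1. Blood is already drawn on Day 1, and registration already waits on an institution-run platelet count, since inclusion 4 uses the Day 1 value and 10.5.1 has it measured locally. The fallback adds one central collection and shipment at Screening B. Week 24 and ET Day 1 need no extra assay if the listed test is run on site. All of this needs a schedule amendment. On-site HCG capability and turnaround must be confirmed with the sites, because the documents do not state them.

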11.3.2 Visit 4 (Week 2)

In principle, subjects should visit the study institution in the morning without taking the morning dose of the study drug.

- Study drug compliance
- ITP Bleeding Score
- Adverse events/concomitant medications
- Vital signs
- Laboratory tests (hematology and serum chemistry)
- Pharmacokinetics (before study drug administration)
- Study drug dispensed (Period I)^{a)}
- Administration of study drug
- Pharmacokinetics (1 to 4 hours after study drug administration)
- a) The need of dispensing the study drug is decided, considering the number of tablets to be taken before the next visit.

11.3.3 Visit 5 (Week 4)

- QOL evaluation (SF-36)^{a)}
- Study drug compliance
- ITP Bleeding Score
- Adverse events/concomitant medications
- ECOG Performance Status
- Vital signs
- Laboratory tests (hematology, serum chemistry, and urinalysis)
- Pharmacokinetics (1 to 4 hours after study drug administration)

- Study drug dispensed (Period I)^{b)}
- a) The QOL evaluation (SF-36) is performed before other procedures and evaluations.
- b) The need of dispensing the study drug is decided, considering the number of tablets to be taken before the next visit.

11.3.4 Visit 6 (Week 6)

In principle, subjects should visit the study institution in the morning without taking the morning dose of the study drug.

- Study drug compliance
- ITP Bleeding Score
- Adverse events/concomitant medications
- Vital signs
- Laboratory tests (hematology and serum chemistry)
- Pharmacokinetics (before study drug administration)
- Study drug dispensed (Period I)^{a)}
- Administration of study drug
- Pharmacokinetics (1 to 4 hours after study drug administration)
- a) The need of dispensing the study drug is decided, considering the number of tablets to be taken before the next visit.

11.3.5 Visit 7 (Week 8)

In principle, subjects should take the morning dose of the study drug 1 to 4 hours before blood sampling and then visit the study institution in the morning.

- Study drug compliance
- ITP Bleeding Score
- Adverse events/concomitant medications
- ECOG Performance Status
- Vital signs
- Laboratory tests (hematology, serum chemistry, and urinalysis)
- Pharmacokinetics (1 to 4 hours after study drug administration)
- Study drug dispensed (Period I)^{a)}
- a) The need of dispensing the study drug is decided, considering the number of tablets to be taken before the next visit.

